Over the past 10 years we have been experiencing increasing difficulty in recruiting subjects with mandibular partial dentures that meet our inclusion criteria. One of the reasons for the failure is the lack of sufficient room in the posterior buccal flange area of the subjects' partial dentures to accommodate two 4 × 4 mm enamel specimens. In an effort to improve subject recruitment we have redesigned the model so that the enamel specimens (4 mm round) are placed in the posterior denture tooth area of their denture and thus eliminate the requirement for having sufficiently large buccal flange area. We have already identified several potential subjects that only qualify for specimen placement in denture teeth and not in the buccal flange area. We have already successfully conducted an in vitro feasibility exercise to demonstrate the practicality of this technique. Furthermore, we have been placing specimens in the denture teeth location for several other in situ model studies including studies using our new biofilm model and this has not presented to be a problem for the subjects. The alteration of the denture teeth does not affect the occlusal part of the artificial tooth and thus does not alter a functional part of the denture.

An additional aspect of the modified model will be to use bovine enamel and not human enamel as has been our usual practice. We are facing increasing difficulty in obtaining a supply of human teeth for our research studies due to a decreasing supply and anticipated regulatory changes requiring informed consent. Most in situ model systems use either bovine or human teeth as the hard tissue substrate. From the perspective of clinical relevance, human teeth would be the most appropriate to use (Zero, 1995). Bovine enamel are known to have structural and chemical differences and to be more porous than human enamel (Lippert et al., 2013) and it is more vulnerable to acid dissolution than human enamel in an artificial caries model systems (Featherstone & Mellberg, 1981; Lippert et al., 2013; Lippert & Lynch, 2014). However, the resulting lesions are practically indistinguishable from each other (Lippert & Lynch, 2014), and these differences result in quantitative differences and not qualitative differences in their response in in situ model studies (Mellberg, 1992; Lippert & Hara, 2012). Bovine enamel can therefore be considered an acceptable alternative to human enamel.

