The purpose of this study is to evaluate the fluoride dose response of different dentifrice fluoride concentrations - 0, 250, 500 and 1100 ppm fluoride of our existing in situ model involving the use of human enamel specimens placed in the buccal flange area of the subjects partial denture with the modified model involving placement of bovine enamel specimens in a denture tooth location.

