2. STUDY DESIGN

This will be a double blind, single center, 4-way crossover design study. Two to three days before the start of each treatment period the subjects will have their teeth cleaned to remove all accessible plaque and calculus and will be provided with a non-fluoride

dentifrice to use until their next visit. At the beginning of each testing period, two gauze-covered 4 × 4 mm partially demineralized human enamel specimens will be placed in the buccal flange area of the subject’s mandibular partial denture. In addition, two gauze-covered 4 mm round partially demineralized bovine enamel specimens will be placed in the buccal surface of two posterior denture teeth of the same side of the partial denture. Once specimens are placed, subjects will wear their partial dentures twenty-four hours a day and use their assigned toothpaste twice daily, as instructed, until their next visit. Specimens will be removed after two weeks and the subjects will undergo a four to five day washout period followed by another cleaning and two to three day lead in period. This process will be repeated until all subjects have used all four test products. Changes in the mineral content of the enamel specimens will be assessed using the SMH and TMR. Enamel fluoride uptake (EFU) will be determined using the microdrill enamel biopsy technique. In addition the net acid resistance (NAR) and the comparative acid resistance (CAR) of the remineralized enamel specimens will be determined.

2.1 Study Schedule:

	Visit 1	Visit 2, 5, 8, 11	Visit 3, 6, 9, 12	Visit 4, 7, 10, 13
	Screening	Prophy	Begin Tx	End Tx
Informed Consent	X			
Medical history review	X	X	X	X
Oral Soft Tissue exam	X	X	X	X
Oral Hard Tissue exam	X	X (v2 only)		X (v13 only)
Salivary Flow	X			
Inclusion/Exclusion criteria	X	X		
Continuance Criteria		X	X	X
Randomization			X	
Adverse Event monitoring		X	X	X
Dental Prophylaxis		X		
Placement of specimens			X	
Removal of specimens				X
Issue washout tooth paste		X		
Return washout tooth paste			X	
Issue study products and diary			X	
Return study products and diary				X
Study close-out				X (v 13 only)

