6.2 Lesion Creation

The square and round enamel specimens will be partially demineralized using a modification of the method described by White [1987]. The 4 x 4 mm human enamel specimens will be immersed for 24 and the 4 mm round bovine specimens will be immersed for 18 hours at 37° C under static conditions in 40 ml of an acid buffer (0.05 mol/L lactate), 50% saturated with respect to hydroxyapatite and with 0.2% (wt/vol) carbopol 907 (BF Goodrich Co., USA) added (pH adjusted to 5.0 using KOH), and then rinsed thoroughly with deionized water. The demineralized enamel specimens will then be stored in a moist environment to prevent dehydration.

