6.4.5 Transverse Microradiography

Sections, approximately 100 µm in thickness, will be cut parallel to the orientation cut (as shown in Figures 2 and 3), after completion of the SMH analysis, using a Silverstone-Taylor Hard Tissue Microtome (Scientific Fabrications Laboratories, USA). The sections will be placed in the TMR-D system and X-rayed at 45 kV and 45 mA at a fixed distance for 12 s. An aluminium step wedge will be X-rayed under identical conditions. The digital images will be analyzed using the TMR software v.3.0.0.18. Sound enamel will be assumed to be 87% v/v mineral.

Lesions will be analyzed after in situ demineralization and the following three parameters calculated:

1. Integrated Mineral Loss - $\Delta Z = [(lesion\ depth \times 87) - area\ under\ the\ curve^*]$
2. Lesion Depth – L (83% mineral i.e. 95% of the mineral content of sound enamel)
3. Maximum mineral density at the surface-zone – SZmax

Note; *area under the curve which relates volume % mineral at distances from the specimen surface with respect to section thickness.

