7. STATISTICAL ANALYSES AND SAMPLE SIZE JUSTIFICATION

7.1 Statistical Analyses

The mean % SMH recovery will be calculated using the five sets of indentations within each enamel specimen. The mean fluoride uptake will be calculated using the four samples within each enamel specimen. The mean % SMH recovery, mean fluoride uptake, mean acid resistance and mean ΔZ , L, SZ_{max} will be computed for the two enamel specimens within a subject for each specimen location (buccal flange or tooth) by treatment; if a subject is missing an enamel specimen, the available enamel specimen will be used. Analyses of fluoride uptake will be performed after using a natural logarithm transformation because the measurements generally are not normally distributed. The validation of the new model will involve two types of evaluations. 1) Analysis level evaluation: The treatments will be compared using analysis of variance models (ANOVA) suitable for a crossover study. The models will include random effects for subject and fixed effects for study period, product, specimen location, and the location-by-product interaction. The random effects will model the correlation and variances over time within a location and the correlation between locations. The primary comparisons of interest will be to determine if the specimens placed in the tooth find the same comparisons to be statistically significant as the specimens placed in the buccal flange. In addition, although likely to be underpowered, the analyses will also include an evaluation of the equivalence of the two locations. This will involve calculating a 95% confidence interval for the ratio between the tooth and buccal flange locations for the relative difference between treatments (treatment difference divided by the positive control mean). A 5% significance level will be used for all tests. No alpha-level adjustments for multiple comparisons adjustments will be applied. 2) Data level evaluation: Agreement between the data from the tooth and buccal flange locations will be evaluated using Bland-Altman plots and intraclass correlation coefficients (ICCs).

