7.2 Sample Size Justification

Based on previous studies we estimate the standard deviation of the differences between treatments in the crossover model to be 10% for % SMH recovery. With a sample size of 24 subjects completing the study, the study will have 80% power to detect a difference between any two treatments of 6% for % SMH recovery, assuming two-sided tests each conducted at a 5% significance level. Due to expected dropouts during the crossover study, the study will enroll 34 subjects.

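### Does section 7.1 need to fix the form of the intraclass correlation and the handling of four pairs per subject before the tooth and flange data are compared?

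*Combined protocol and SAP*

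**What the plan says.** Section 7.1 validates the modified model in two ways. The first, the analysis-level evaluation, is a crossover ANOVA with random subject effects and fixed effects for period, product, location and location-by-product. It holds the primary comparisons: whether the tooth specimens find the same product differences significant as the flange specimens. It also gives a 95% confidence interval for the tooth-to-flange ratio of relative treatment differences. The second, the data-level evaluation, is one sentence: "Agreement between the data from the tooth and buccal flange locations will be evaluated using Bland-Altman plots and intraclass correlation coefficients (ICCs"). Neither method is mentioned anywhere else.

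The unit of data is stated. Means "will be computed for the two enamel specimens within a subject for each specimen location (buccal flange or tooth) by treatment". Since "This will be a double blind, single center, 4-way crossover design study", each completer contributes four tooth-flange pairs per outcome. The reference to treatment there defines how specimen means are formed; it does not say that ICCs are computed within treatment. The natural-log scale for fluoride uptake is set earlier in the same section, ahead of both evaluations.

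**The concern.** Three choices are open: the ICC type, pooled or by treatment, and the treatment of repeated pairs. Each can move the result.

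- **Pooling.** The study is meant to "evaluate the fluoride dose response of different dentifrice fluoride concentrations" (0, 250, 500 and 1100 ppm), so the doses are there to spread the means. That spread enters a pooled ICC as agreement. A by-treatment ICC reflects only subject-level agreement within a dose.
- **Type.** Section 1 says of human and bovine enamel that "these differences result in quantitative differences and not qualitative differences in their response in in situ model studies". A constant shift lowers an absolute-agreement ICC and leaves a consistency ICC untouched.
- **Offsets by endpoint.** % SMH recovery and the two acid-resistance measures are scaled to each specimen's own initial softening. The microradiography outcomes are not. Section 6.4.5 says "Lesions will be analyzed after in situ demineralization and the following three parameters calculated" and describes no pre-exposure value, while section 6.2 has "human enamel specimens will be immersed for 24 and the 4 mm round bovine specimens will be immersed for 18 hours". A substrate offset unrelated to product could enter ΔZ, L and SZmax directly.
- **Repeated pairs.** Treating 24 × 4 = 96 pairs as independent would overstate the precision of a mean shift.

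At stake is whether a reported agreement figure could be chosen after seeing the data, and whether a reader could interpret it.

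**Working it through.** **The plan's own figure.** Section 7.2 says "we estimate the standard deviation of the differences between treatments in the crossover model to be 10% for % SMH recovery". With 24 completers, a 6-point difference and a two-sided 5% test, a paired t-test has noncentrality 6/10 × √24 = 2.94 on 23 df and power 80.4%. The stated 80% reproduces. It concerns treatment differences, not agreement.

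**Inputs for the ICC illustration.** From section 7.2, residual variance per location = 10²/2 = 50, taking errors in different periods as independent. Assumed, because the documents give no values:

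- dose means in equal 6-point steps, so V = (81 + 9 + 9 + 81)/4 = 45
- location offset d = 10, so d²/2 = 50
- within-dose correlation between locations r = 0.5
- between-subject variance 0, 50 or 150, so within-dose variance s² = 50, 100 or 200

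**Formulas and results**

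| ICC version | Formula | s² = 50 | s² = 100 | s² = 200 |
|---|---|---|---|---|
| Pooled, consistency | (V + r·s²)/(V + s²) | 70/95 = 0.74 | 95/145 = 0.66 | 145/245 = 0.59 |
| Pooled, absolute | (V + r·s²)/(V + s² + d²/2) | 70/145 = 0.48 | 95/195 = 0.49 | 145/295 = 0.49 |
| By treatment, consistency | r | 0.50 | 0.50 | 0.50 |
| By treatment, absolute | r·s²/(s² + d²/2) | 25/100 = 0.25 | 50/150 = 0.33 | 100/250 = 0.40 |

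**How far the assumptions drive this.** The third row is the assumed r restated. With 2-point steps (V = 5), pooled consistency is 30/55 = 0.55, 55/105 = 0.52 and 105/205 = 0.51, so the pooling effect nearly disappears.

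Holding r at 0.5 also changes the covariance structure from column to column. If instead subject effects are fully shared by the two locations and residuals are independent, then r = (s² − 50)/s² and, with V = 45:

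| | s² = 50 | s² = 100 | s² = 200 |
|---|---|---|---|
| By treatment, consistency | 0 | 0.50 | 150/200 = 0.75 |
| Pooled, consistency | 45/95 = 0.47 | 95/145 = 0.66 | 195/245 = 0.80 |
| Gap | 0.47 | 0.16 | 0.05 |

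By-treatment absolute agreement in the last column becomes 150/250 = 0.60 instead of 0.40. The gap can be large or trivial, and the documents do not say which.

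**Precision.** For a by-treatment ICC of 0.50 in 24 subjects, F = (1 + 0.5)/(1 − 0.5) = 3, and the 97.5% point of F(23, 23) is 2.31. The 95% limits are (3/2.31 − 1)/(3/2.31 + 1) = 0.13 and (3 × 2.31 − 1)/(3 × 2.31 + 1) = 0.75. At s² = 100, the values from 0.33 to 0.66 all lie inside that interval.

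**Repeated pairs.** If a share c of the difference variance lies between subjects, the standard error of a mean shift from 96 supposedly independent pairs is too small by √(1 + 3c): 1.14 at c = 0.1 and 1.58 at c = 0.5. The limits of agreement barely move. The expected variance of the 96 differences is σ²[(1 − c) + c × 92/95]. With an assumed σ² = 100 and c = 0.5 this is 98.4, giving a half-width of 1.96 × √98.4 = 19.4 against the correct 1.96 × 10 = 19.6.

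**The case for a change.** The strongest case for amending the plan is that this is one of only two evaluations offered as validation. In the first table the same data could be reported as 0.74 or 0.25, and two or three sentences would close the choice at no cost. Nor is either version enough alone. If the tooth showed no dose response at all (equal overall means), by-treatment consistency would stay at 0.50, while pooled consistency, r·s²/(s² + V/2), would be 25/72.5 = 0.34, 50/122.5 = 0.41 and 100/222.5 = 0.45. Saying that a statistician can choose later is uncomfortable when the choice may follow sight of the data.

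What stands is that the text is silent and that an unlabelled ICC would be hard to read. The rest weakens on inspection:

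- There is no threshold to pass, so a favourable choice cannot turn failure into success. Loss of dose response in the tooth would show in the primary product comparisons and the location-by-product term.
- The standard-error factor applies to an inference the plan does not announce. Section 7.1 plans Bland-Altman plots. The mean location shift can be taken from the mixed model, whose random effects cover correlation over time and between locations.
- The offset argument is one-sided. Section 6.4.1 applies the same indentation-length windows, 43 ± 3 µm sound and 120 ± 20 µm after demineralization, without distinguishing substrate. Section 1 also describes the lesions in the two substrates as nearly alike, and says bovine enamel dissolves more readily, which fits the shorter immersion. Matching on hardness does not guarantee matching on ΔZ, so an offset remains possible, but the plot would show it.

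**Conclusion.** The gap is genuine, but it is one that analysts fill sensibly. No stated rule gives a wrong answer, and no conclusion of the study rests on which ICC is used: the primary comparison and the ratio interval do not depend on it. The two planned tools also complement each other, because the plot shows the offset that a consistency ICC leaves out. Ordinary practice is to name the ICC form, show by-treatment or product-adjusted values with intervals beside any pooled value, and either plot by treatment or allow for repeated pairs. That can all be done at reporting, with no new data.

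On size, the versions differ by anything from 0.05 or less to nearly 0.5, depending on dose spread, offset and correlation, which the documents do not give. With 24 subjects a single by-treatment ICC of 0.50 is known only to within 0.13 to 0.75. This judgement rests on the evaluation staying descriptive. If an acceptance threshold for the ICC were attached, its form would have to be fixed in advance.

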7.2 Sample Size Justification

Based on previous studies we estimate the standard deviation of the differences between treatments in the crossover model to be 10% for % SMH recovery. With a sample size of 24 subjects completing the study, the study will have 80% power to detect a difference between any two treatments of 6% for % SMH recovery, assuming two-sided tests each conducted at a 5% significance level. Due to expected dropouts during the crossover study, the study will enroll 34 subjects.

8. DATA QUALITY ASSURANCE

This study will be conducted in compliance with the US Code of Federal Regulations (CRF) governing informed consent (21 CFR 50), Institutional Review Board (IRB) (21 CFR 56), and with applicable regulations governing Investigator conduct (21 CFR 312).

9. OBLIGATION OF THE INVESTIGATOR

9.1 Advertising

All potential advertising materials used to recruit subjects for this study will be submitted to the relevant IRB.

9.3 Subject Consent

Written informed consent will be obtained from all subjects prior to their enrollment into the study. The consent form will comply with all applicable regulations governing protection of the participants in the study, and include basic elements specified in the US. Code of Federal Regulations, 12 CFR 50.25(a). A signed copy of the consent form will be given to the subject and the original one will be retained by the Investigator. In order to ensure confidentiality, the Investigator will store the consent forms separate from the CRFs.

9.4 Data Collection

Data will be collected on source documents/CRFs created by the Investigator.

9.4.1 Case Report Forms

Case report forms will be used for recording all data not entered directly into computers. The Investigator will be responsible for maintaining original consent forms, CRFs and other source documentation.

The CRFs that will be used, unless otherwise indicated are:

- Inclusion/Exclusion Criteria
- Continuance Criteria
- Oral soft tissue
- Oral hard tissue
- Adverse event
- Serious adverse event
- Subject Accountability

9.5 Adherence to Protocol

The final protocol constitutes the conduct of the study. The Investigator is required to adhere to this final protocol. Any reasonable alternatives, variations, or deviations from the protocol must first be approved by the IRB. Any clarification to the protocol will be documented in the study file.

9.6 Records Retention

At the conclusion of the study, all records, relevant medical/dental records, copies of CRFs, and informed consent forms for all subjects treated with the drug or employed as a control in the study are retained by the Investigator for a period of time not less than 10 years.

9.7 Investigator's Final Report

Following the completion of the study the Investigator shall prepare an integrated clinical and final study report. The final report will include a general description of the conduct of the study including protocol deviations, subject withdrawals, a discussion of AEs, safety data, and laboratory analysis. This report will be approved and signed by the Investigator.

